12. STATISTICAL ANALYSIS

- *Describe how your data will be used to test the hypotheses.*
- *State clearly what variables will be tested and what statistical tests will be used.*
- *Include sample size calculations.*

- *If this is a pilot study, state which variables will be examined for hypothesis generation in later studies.*

In general, baseline patient characteristics including demographics and clinical data will be summarized using descriptive statistics for all data combined and data by treatment arm. Specifically, continuous variables will be summarized using mean, standard deviation and median; categorical variables will be summarized using frequencies and percentage. No inferential comparison of treatment arms will be made with respect to baseline and demographic clinical data; such comparisons will be descriptive only. Unless otherwise specified, all results will be considered significant if $p < 0.05$. All data analysis will be performed using SAS 9.4 (SAS institute Inc., Cary, NC). The intent-to-treat (ITT) principle will be employed, i.e all randomized patients in the groups to which they are randomly assigned will be included in the final analysis, regardless of the intervention they actually receive, and regardless of withdrawal from treatment or deviation from the protocol for any reason.

The primary endpoint is all-cause mortality at 28 days. It will be compared between the two treatment arms using chi-squared test or Fisher's exact test.

Among the secondary study endpoints, binary variables (need for ICU admission, need for higher oxygen supplementation including non-rebreather mask, high flow nasal cannula or non-invasive mechanical ventilation, need for invasive mechanical ventilation and need for oxygen supplementation upon discharge) will be compared using chi-squared test or Fisher's exact test between the two arms; continuous variables (ICU length of stay, hospital length of stay, duration of mechanical ventilation) will be compared between the two arms using Kaplan-Meier curve and log-ran test to take into account data censoring.

Sample size consideration: The sample size calculation was based on the hypothesis of primary endpoint. Our primary hypothesis is that the use of a higher dose of dexamethasone equivalent to 1 mg/kg/day of methylprednisolone would be associated with a decrease in mortality in COVID-19 patients requiring oxygen supplementation. A two group χ^2 test with a 5% two-sided significance level will have 80% power to detect the difference between the proportion of dexamethasone 6 mg group 23.3% and the proportion of dexamethasone weight based 5.9% (odds ratio of 0.206) when the sample size in each group is 64.

To account for 10% dropout rate, will be increasing recruitment to 142, with 71 in each arm to ensure 128 evaluable subjects.

Missing data: If there is less than 5% of an endpoint missing, complete case analysis will be used; if there is more than 5% missing, sensitivity analysis will be performed by assuming all the missing values of an endpoint to be either outcome if it is binary, or by assuming all the missing values of an endpoint to be either upper quartile or lower quartile of the available values if it is continuous, to see if the results are similar to those using complete case analysis.

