10. ENDPOINTS

- *Describe the primary and secondary study endpoints*
- *Describe any primary or secondary safety endpoints*

Primary study endpoint: all-cause mortality at 28 days.

Secondary study endpoints: need for ICU admission, ICU length of stay, hospital length of stay, higher requirements of oxygen supplementation (venturi mask, non-rebreather mask, high-flow nasal cannula or non-invasive mechanical ventilation), invasive mechanical ventilation, duration of invasive mechanical ventilation, ECMO, tracheostomy, subjective symptoms at 28 days, disposition upon discharge, and oxygen supplementation upon discharge.

The primary and secondary safety endpoints will include the development of secondary bacterial or fungal infections that is objectively identified based on culture data, and clinically significant hyperglycemia requiring ICU stay or insulin drip.

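### The p < 0.05 rule covers all results, with no multiplicity control or exploratory label for the secondary endpoints; across the 7 named secondary tests the chance of a false positive is up to about 30%

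*Combined protocol and SAP*

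**What the plan says.** Section 12 (Statistical Analysis) gives a single criterion: "Unless otherwise specified, all results will be considered significant if" p < 0.05. No other criterion is given later for any secondary endpoint.

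The same section assigns tests to 7 secondary endpoints:

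- Four are binary: ICU admission, higher oxygen supplementation, invasive mechanical ventilation, and oxygen at discharge. The passage begins "Among the secondary study endpoints, binary variables (need for ICU admission, need for higher oxygen supplementation", and the test is chi-squared or Fisher's exact.
- Three are durations: ICU stay, hospital stay, and time on mechanical ventilation. They are compared by Kaplan-Meier curves and the log-rank test.

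Section 4 lists 13 secondary outcomes. Section 10 gives the efficacy list ("Secondary study endpoints: need for ICU admission, ICU length of stay, hospital length of stay, higher requirements of oxygen supplementation" and so on) and places secondary infections and clinically significant hyperglycemia under safety. Six of the 13 have no named test: ECMO, tracheostomy, secondary infections, hyperglycemia, subjective symptoms and disposition.

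There is one primary endpoint, 28-day all-cause mortality, and the sample size rests on it: "A two group χ^2 test with a 5% two-sided significance level will have 80% power".

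For baseline characteristics, section 12 expressly rules out inferential comparison of the arms. It says nothing similar about the secondary endpoints.

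**The concern.** Naming one primary endpoint protects the mortality claim. It does not limit what else may be called significant, because the stated rule reaches all results. A trial that follows the plan as written could report any of the 7 secondary tests as a significant finding on an unadjusted p-value. Readers would have no means in the plan of telling a confirmatory result from a chance one.

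What is at stake is the credibility of secondary claims about ICU use, oxygen escalation, ventilation and length of stay. The validity of the mortality comparison is not at stake.

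**Working it through.** **The plan's own figure.** The inputs in section 12 are "the proportion of dexamethasone 6 mg group 23.3"%, "the proportion of dexamethasone weight based 5.9% (odds ratio of 0.206"), two-sided 5% and 80% power. With the pooled chi-squared formula and mean proportion (0.233 + 0.059)/2 = 0.146:

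n = [1.960 × √(2 × 0.146 × 0.854) + 0.842 × √(0.233 × 0.767 + 0.059 × 0.941)]² / (0.233 − 0.059)² = 63.4, rounded up to 64 per arm.

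Power at 64 per arm is 80.3%, and the odds ratio is (0.059/0.941)/(0.233/0.767) = 0.206. The stated size, "when the sample size in each group is 64", is reproduced. It concerns the primary test only. The plan gives no family-wise error rate for the secondary tests to compare with what follows.

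**Inputs for the secondary tests.** The number of tests is 7 (section 12: 4 binary and 3 log-rank). The threshold is 0.05 per test (section 12). I take the tests as two-sided, so 0.025 falls in each direction. The correlation between endpoints is not given, so I assume a common value from 0 to 0.7.

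**Independent tests, no true effect.**

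- At least one significant result in either direction: 1 − 0.95⁷ = 0.302.
- At least one significant result favouring the higher dose: 1 − 0.975⁷ = 0.162.
- Expected number of false positives: 7 × 0.05 = 0.35.

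**Correlated tests.** Simulation of 7 equicorrelated normal statistics, 400,000 draws, critical value 1.960:

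| Assumed correlation | Either direction | Favouring higher dose |
|---|---|---|
| 0 | 30.2% | 16.3% |
| 0.3 | 27.1% | 13.7% |
| 0.5 | 22.9% | 11.5% |
| 0.7 | 17.8% | 8.9% |

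The row for zero correlation agrees with the formulas to within simulation error.

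**Effect of Fisher's exact test.** The exact null rejection rate at 64 per arm, computed for event rates of 2% to 50%, is about 0.1% to 3.1% for Fisher's test and about 2.2% to 5.1% for chi-squared. If all four binary endpoints use Fisher at its highest computed rate, and the three log-rank tests hold 5%, the chance of a false positive in either direction is 1 − 0.969⁴ × 0.95³ = 0.244 before any correlation. The plan allows either test, so 30% is an upper figure.

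**The case against.** The strongest reply is that the plan does separate its endpoints. It has one primary endpoint, one primary hypothesis and a sample size built on that hypothesis, and the p < 0.05 sentence sits among general conventions such as software and the intention-to-treat principle. This stands in part: the primary test's error rate is untouched by the secondary testing. It does not answer the point, because the rule is written for all results and nothing withdraws it for the secondaries, whereas the same section does withdraw inference for baseline data.

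Three stronger readings are tempting, and the documents do not support them.

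- *A reader might infer that a chance benefit of the higher dose is likely.* It is not. The 30% includes results in the direction of harm. The favourable-direction figure is about 16% at most for the 7 named tests, and lower with positive correlation. Such correlation is plausible, since ICU admission, ventilation and length of stay overlap.
- *A reader might count all 13 outcomes in section 4.* Under independence that gives 1 − 0.95¹³ = 0.487 in either direction and about 28% in favour of the higher dose. But six of the 13 have no named test, and two of those six are safety endpoints that should stay outside any correction. Even this figure is below one half.
- *A reader might infer that the primary will probably miss significance and that the report will then rest on a secondary.* The first part depends on the true effect, which the documents do not give. Under the planned effect the power is 80%. The second part predicts reporting behaviour that no section describes.

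**Conclusion.** The concern holds in a limited form. The plan applies p < 0.05 to all results and gives no hierarchy, correction or exploratory label for the secondary endpoints. This is more than a missing detail, because the stated rule would itself turn an unadjusted secondary p-value into a significant finding.

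Across the 7 named tests the family-wise false-positive chance is up to about 30% in either direction, of which about 16% is the chance of a result favouring the higher dose. Allowing for assumed correlations of 0.7 to 0.3, it is about 18% to 27%, or 9% to 14% in favour of the higher dose. Even the lowest of the either-direction figures is more than three times the 5% applied to each single test.

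These figures assume no true effect on any endpoint, two-sided tests that hold their nominal level, and one common correlation. Fisher's test would lower them. They do not include the interim looks at 20, 50 and 100 patients, which are a separate matter. The point is worth correcting because correction is cheap; it does not call the primary analysis into question.

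**What to change.** Replace the general significance sentence in section 12 with:

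> Day-28 all-cause mortality is the only confirmatory test, at the two-sided 5% level subject to whatever is specified for the interim analyses in section 11. Secondary efficacy endpoints are exploratory and are reported as effect estimates with 95% confidence intervals, without claims of statistical significance. Safety endpoints are reported without multiplicity correction.

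The reference to section 11 is needed because that section plans an interim analysis of results as well as safety. The new sentence should not promise a full 5% at the end without regard to it.

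The cost is three sentences of analysis text and no extra patients or data. The downside is that no secondary result can be called significant. If confirmatory secondary claims are wanted, a Holm procedure over the 7 named tests, or testing them only after a significant primary result, would be a reasonable choice. Neither is needed otherwise.

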6. RECRUITMENT METHODS

- *Describe the source of potential subjects*
- *Describe the methods that will be used to identify potential subjects*
- *Describe any materials that will be used to recruit subjects. A copy of any advertisements (flyers, radio scripts, etc.) should be submitted along with the protocol.*
- *If monetary compensation is to be offered, this should be indicated in the protocol*

Recruitment of potential subjects will occur at 7 of the hospitals within the Northwell Health System including Long Island Jewish Medical Center, North Shore University Hospital, Plainview Hospital, Long Island Jewish Valley Stream Hospital, Lenox Hill Hospital, South Shore Hospital and Mather Hospital. Enrollment will first be done at North Shore University Hospital and Long Island Jewish Medical Center with phased-approach expansion to the other sites.

Patients that are admitted with COVID-19 infection within these institutions will be screened for eligibility. The principal investigator and co-investigators will be responsible in obtaining informed consent from those patients who meet eligibility criteria in order to participate in the study. A full discussion of the rationale of the study will be held with the patients and/or their surrogate decision makers to answer any study-related questions. The use of a printed/electronic version of the informed consent will be available for review. All research coordinators will be trained by the principal investigator on non-coercive recruitment approaches. Patients will be clearly informed that their medical care will be of the highest standards regardless of their decision to participate on the study.

No monetary compensation will be offered.

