11. RESEARCH PROCEDURES

- *Include a detailed description of all procedures to be performed on the research subject and the schedule for each procedure.*
- *Include any screening procedures for eligibility and/or baseline diagnostic tests*
- *Include procedures being performed to monitor subjects for safety or minimize risks*
- *Include information about drug washout periods*
- *If drugs or biologics are being administered provide information on dosing and route of administration*
- *Clearly indicate which procedures are only being conducted for research purposes.*
- *If any specimens will be used for this research, explain whether they are being collected specifically for research purposes.*
- *Describe any source records that will be used to collect data about subjects*
- *Indicate the data to be collected, including long term follow-up*

All hospitalized patients with COVID-19 infection documented by a positive PCR test who require oxygen supplementation or have documented hypoxemia based on oxygen saturation <94% will be screened for eligibility. Baseline diagnostics tests will be as per standard of care and no additional testing is required for our research purposes. All patients will receive routine medical care as per most updated COVID-19 guidelines prior to randomization.

Eligible patients who agree to participate in the study will be randomized 1:1 into two groups. Randomization was set up in REDCap. Once the patient gives consent, the randomization form on REDCap will randomize to either of the groups. As the study is multi-site, the randomization will be stratified by each site.

The standard dexamethasone group will receive a dose of 6 mg daily. The higher dexamethasone group will receive a dose of 0.2 mg/kg/day with maximum dose of 20 mg per day. The route of administration will be IV for both groups. No patients will receive less than dexamethasone 6 mg. The duration of treatment in both arms will be a total of 10 days of steroids or until discharge, whichever comes first.

No procedures, blood draws, imaging or diagnostic testing will be performed on the participants other than those indicated for their medical care.

Data will be obtained from the medical electronic records and tabulated in REDCap. Patient will be de-identified and REDCap access will be limited to appropriate investigators involved in the trial to avoid HIPAA violations.

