Data to be collected will include baseline demographic variables, need for higher requirements of oxygen supplementation (venturi mask, non-rebreather mask, high flow nasal cannula or non-invasive mechanical ventilation), ICU admission, invasive mechanical ventilation, duration of invasive mechanical ventilation, tracheostomy, ECMO, length of ICU stay, length of hospital stay, development of secondary bacterial or fungal infections, subjective symptoms at 28 days, development of clinically significant hyperglycemia, oxygen supplementation upon discharge and disposition upon discharge (home, home with physical therapy, skilled nursing facility, long-term acute care facility, long-term care facility / nursing home, acute rehabilitation facility, hospice care, death)

An interim safety and result analysis will be performed after the first 20 patients are enrolled in the study. Subsequent monitoring will occur when 50 and 100 patients are recruited. A designated committee from the study will be assigned for this purpose.]

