We are going to include vulnerable populations such as elderly patients, cognitively impaired patients, poor/uninsured and minorities as long as they meet eligibility criteria for the study. We will ensure that the recruitment procedures include language translation, the participants are not coerced and that participants or surrogate decision makers understand the consent process and research protocol.

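### Randomization is stratified by site, but the primary mortality test ignores site and is left as chi-squared or Fisher's with no rule for choosing

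*Combined protocol and SAP*

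**What the plan says.** Section 11 (Research Procedures): "As the study is multi-site, the randomization will be stratified by each site". Section 6 (Recruitment Methods): "Recruitment of potential subjects will occur at 7 of the hospitals", starting at two of them "with phased-approach expansion to the other sites". Site sizes are therefore likely to be uneven, although the protocol gives no numbers per site.

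Section 12 (Statistical Analysis) gives the primary comparison in one sentence: "It will be compared between the two treatment arms using chi-squared test or Fisher's exact test". The only stated use of baseline data is that "baseline patient characteristics including demographics and clinical data will be summarized using descriptive statistics". The sample-size paragraph of the same section assumes a two-group chi-squared "test with a 5% two-sided significance level will have 80% power to detect the difference" between 23.3% and 5.9% mortality with 64 per arm, and raises recruitment to 71 per arm for 10% dropout.

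No section contains a site-stratified or site-adjusted analysis, a covariate for the primary endpoint, a rule for choosing between the two tests, or a statement on continuity correction. That sites are pooled is inferred from the absence of a site term. With phased opening, fewer than seven sites may contribute.

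**The concern.** When randomization is stratified by a factor, the primary analysis should normally take account of that factor. If mortality differs between hospitals and the test ignores it, the standard error is too large for the design and the test becomes conservative.

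The second gap is that two tests with different power are both permitted. The trial was sized on one of them, and the other can miss the stated 80%. Some data sets would be significant by one test and not by the other.

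Timing adds to this. Section 11 plans an analysis of results as well as safety after 20 patients, and section 15 says the monitoring committee is not independent and includes co-investigators. Study staff could therefore see outcome data while the primary test is still open.

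**Working it through.** **Inputs.** From section 12: control mortality p1 = 0.233, high-dose mortality p2 = 0.059, two-sided alpha 0.05, power 80%, 64 per arm evaluable, 71 per arm recruited. From section 6: seven sites.

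**1. Reproducing the plan's figure.** With p̄ = (0.233 + 0.059)/2 = 0.146 and difference d = 0.174:

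n = [1.960·√(2·0.146·0.854) + 0.8416·√(0.233·0.767 + 0.059·0.941)]² / 0.174² = (0.9787 + 0.4073)² / 0.030276 = 63.46, rounded up to 64.

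With a continuity correction, n = (63.46/4)·[1 + √(1 + 4/(63.46·0.174))]² = 74.5, rounded up to 75. The stated 64 is therefore correct, but only for the uncorrected test.

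**2. Exact power of the candidate tests**, from enumerating two independent binomials:

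| Per arm | Pearson, uncorrected | Chi-squared, corrected | Fisher | Pearson significant, Fisher not |
|---|---|---|---|---|
| 64 | 82.3% | 75.6% | 75.6% | 6.8% |
| 71 | 86.5% | 80.8% | 81.1% | 5.4% |

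At both sizes, no table has Fisher significant and Pearson not.

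Example: 12 versus 4 deaths of 64. Pearson χ² = 128·(12·60 − 4·52)²/(64·64·16·112) = 4.57, p = 0.033. Corrected χ² = 3.50, p = 0.061. Fisher p = 0.059.

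**3. Effect of the missing rule.** Expected deaths at 64 per arm are 14.9 + 3.8 = 18.7, so the smallest expected count is about 9.3. A rule that uses Fisher only when an expected count is below 5 would select it in 0.6% of trials at 64 per arm and 0.14% at 71. A rule based on an observed count below 5 would be met by the high-dose deaths alone in 67% and 59%. The plan states neither rule.

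**4. Type I error.** Over null mortality 5.9% to 23.3%, exact Pearson error is 4.8–5.1% at 64 per arm and 4.9–5.2% at 71. Fisher's is 1.5–3.0% and 1.7–3.2%. Choosing between the two after seeing the data cannot add false positives beyond Pearson's, because every Fisher rejection is also a Pearson rejection.

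**5. Ignoring or using site.** This was simulated with 400,000 trials per scenario. Assumptions not in the documents: permuted blocks of 4, sites under 10 patients pooled, and either uneven site sizes (50/40/18/14/10/6/4 for 142; 45/36/16/13/9/5/4 for 128) or near-equal ones. Site effects are normal on the logit scale. Power, Pearson then uncorrected Mantel-Haenszel:

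| Site SD | Uneven, 142 | Near-equal, 142 | Uneven, 128 | Near-equal, 128 |
|---|---|---|---|---|
| 0 | 86.7, 86.4 | 86.6, 86.4 | 83.0, 82.6 | 83.0, 82.5 |
| 0.5 | 86.0, 86.1 | 86.4, 86.7 | 82.5, 82.6 | 82.7, 82.8 |
| 1.0 | 85.1, 86.1 | 86.3, 87.7 | 81.6, 82.7 | 82.6, 84.3 |

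From unrounded values, Mantel-Haenszel minus Pearson is −0.2 to −0.5 points at SD 0, +0.1 to +0.2 at 0.5 and +1.1 to +1.7 at 1.0. At null mortalities of 8%, 14.6% and 23.3%, Mantel-Haenszel error stays at 4.7–5.0%. Pearson's is 5.0–5.2% at SD 0, 4.6–5.0% at 0.5 and 3.8–4.5% at 1.0. With a continuity correction, Mantel-Haenszel power falls to 74.3–76.2% (128 patients) and 79.0–81.1% (142), so the correction must be excluded explicitly.

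**6. Baseline covariate.** A Firth logistic model with a normal, age-like covariate at 71 per arm changes power relative to Pearson by −0.5, −0.1, +1.5 and +4.0 points for assumed log-odds per SD of 0, 0.4, 0.8 and 1.2. Its type I error is 4.7–4.9%.

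**The case against.** The 75.6% figure is a worst case. It needs Fisher or the correction to be used always, the full 10% to be lost, and exactly equal arms. Section 12 specifies intention-to-treat, and section 20 (Privacy) provides an email survey and then a phone call to obtain the primary endpoint. With all 71 per arm, every candidate test exceeds 80%. Exact balance also makes Fisher unusually coarse: at 66/62, 62/66 and 68/60 (control/high dose), Fisher's power is 79.7%, 78.5% and 77.8%, against Pearson's 82.7%, 83.6% and 81.9%. This stands for Fisher, where the gap narrows to about 3–5 points. It does not rescue the corrected chi-squared test, which has 73.6–75.1% at those splits.

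Under the usual expected-count convention, the final decision would differ from Pearson's in only about 0.05% of trials at 64 per arm, and the sample-size paragraph already points to chi-squared. That also stands: the open wording alone is a matter of missing detail.

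The gain from stratifying by site is small, depends on an assumed site SD, and the hospitals belong to one health system. At 20 patients only about 3 deaths are expected (20 × 0.146 = 2.9), so that look could hardly guide the choice of test. Both points are fair. They limit the size of the problem, but they are not a reason to leave the stratification factor out of the analysis.

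**Conclusion.** The concern holds as a moderate one that should be addressed; it is not an error in validity. The sample size is right for the test it assumes, and neither ignoring site nor the open choice of test raises false positives above those of uncorrected Pearson.

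What is missing is a primary analysis that follows the stratified design, and a single fixed test. The site-stratified test keeps error near 5% across the assumed range of site differences, costs at most about half a point of power if sites do not differ, and gains 1 to 2 points if they differ strongly. Fixing the uncorrected form avoids a loss of up to 6.8 points at 64 per arm with equal arms (82.3% against 75.6%).

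The test comparisons depend only on the plan's own rates and numbers. The site results rest on assumed site sizes, block size and site SD, and the covariate results on an assumed prognostic strength. The documents give none of these, so confidence in the size of those gains is moderate.

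**What to change.** In section 12, before the 20-patient analysis:

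- Name one primary test: Mantel-Haenszel stratified by site, without continuity correction, reported with the stratified risk difference and its 95% confidence interval.
- Fix a rule for pooling small sites by number randomized, for example pooling those with fewer than 10.
- Keep uncorrected Pearson chi-squared as the unadjusted supportive analysis, with Fisher's exact test only if an expected count in the overall table is below 5.
- In the sample-size paragraph, state that the unstratified, uncorrected chi-squared calculation approximates the stratified test.
- Optionally, pre-specify one supportive Firth logistic model adjusted for age. This suits the 19 to 21 deaths expected (64 × 0.292 = 18.7; 71 × 0.292 = 20.7). Age should already be available, since section 11 states "Data to be collected will include baseline demographic variables". Oxygen support at randomization could be a second covariate if it is recorded.

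The cost is wording and a little extra analysis, with no additional patients, procedures or required data. The downsides are about 0.2–0.5 points of power in the primary test if sites do not differ at all, and about 0.5 points in the supportive model if age is not prognostic.

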4. OBJECTIVE(S)/SPECIFIC AIMS AND HYPOTHESES

- *A concise statement of the goal(s) of the current study.*
- *The rationale for and specific objectives of the study.*
- *The goals and the hypothesis to be tested should be stated.*

The aim of the study is to compare the efficacy of dexamethasone at the current recommended dose versus a higher, weight-based dose. We hypothesize that the use of a higher, weight-based dose of dexamethasone equivalent to 1 mg/kg/day of methylprednisolone would be associated with a decrease in mortality in COVID-19 patients requiring oxygen supplementation.

Primary outcome:

- All-cause mortality at 28 days

Secondary outcomes:

- ICU admission
- ICU length of stay
- Hospital length of stay
- Need for higher oxygen supplementation including venturi mask, non-rebreather mask, high flow nasal cannula or non-invasive mechanical ventilation
- Invasive mechanical ventilation
- Duration of invasive mechanical ventilation
- ECMO
- Need for tracheostomy
- Development of secondary bacterial or fungal infections
- Development of clinically significant hyperglycemia, which will be defined as need for insulin drip or ICU admission to control hyperglycemia
- Oxygen supplementation upon discharge from the hospital
- Subjective symptoms at 28 days
- Disposition upon discharge (home, home with physical therapy, skilled nursing facility, long-term acute care facility, long-term care facility / nursing home, acute rehabilitation facility, hospice care, death)

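### Oxygen supplementation at discharge is tested as yes/no in all randomized patients, but the plan does not say how patients who die before discharge count

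*Combined protocol and SAP*

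**What the plan says.** Section 4 lists "Oxygen supplementation upon discharge from the hospital" as a secondary outcome, and Section 10 repeats it. Section 12 places it with the binary variables to be compared by arm: "need for invasive mechanical ventilation and need for oxygen supplementation upon discharge) will be compared using chi-squared test or Fisher's exact test between the two". The same section applies intention to treat, with all randomized patients in the final analysis.

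The sample-size paragraph of Section 12 supplies the expected 28-day mortality: "proportion of dexamethasone 6 mg group 23.3% and the proportion of dexamethasone weight based 5.9" per cent.

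Three other provisions bear on the point:

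- Death is a category of disposition upon discharge (Sections 4 and 11), which is a separate item.
- The allowance for censoring in Section 12 covers only lengths of stay and duration of ventilation.
- The missing-data rule in Section 12 uses complete cases when less than 5% of an endpoint is missing. Above 5% it adds sensitivity analyses that set all missing binary values to one outcome and then the other, for comparison with the complete-case result. It does not mention death.

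**The concern.** Oxygen status at discharge exists only for patients who leave hospital alive. The plan nevertheless calls for a two-by-two test in everyone randomized, so someone has to decide what to do with the deaths. Both natural choices are unsound.

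- **Deaths coded as no oxygen.** Death then counts as the favourable result, and the arm with more deaths gains.
- **Deaths left out.** The comparison is between survivors, a group that treatment itself helps to select. If the higher dose saves patients, its survivors include people who would have died on 6 mg, and these may be sicker than the rest.

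The trial is built on a large mortality difference, so the affected patients are expected to be very unequal between arms. At stake is whether this result can be read alongside the mortality result, and whether its direction is set by a coding choice made after the data are seen.

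**Working it through.** **Inputs from Section 12.** Mortality 23.3% (6 mg) and 5.9% (weight-based); 64 evaluable and 71 enrolled per arm; two-sided 5% level.

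**Assumed, because the documents give no figure.** The oxygen rate at discharge among survivors (q), and the rate among the extra patients saved by the higher dose (r).

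**1. The plan's own figure.** A two-group chi-squared test with pooled variance and no continuity correction, 23.3% v 5.9%, needs 64 per arm (power 80.3%). The odds ratio is (0.059/0.941)/(0.233/0.767) = 0.206. Both agree with the plan, so these rates are a sound basis for what follows.

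**2. Patients without a value.** 71 × 0.233 = 16.5 and 71 × 0.059 = 4.2, or about 17 v 4 (at 64 per arm, 14.9 v 3.8). Overall this is (23.3% + 5.9%)/2 = 14.6% of patients, with a gap of 17.4 points between arms. These are all deaths by day 28. If only half of them occur before discharge, 7.3% of patients lack a value. The share falls below the plan's 5% threshold only if fewer than 0.05/0.146 = 34% of deaths occur before discharge.

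**3. Deaths coded as no oxygen, same q in both arms.** The rates are 0.767q v 0.941q, a difference of 0.174q against the higher dose although oxygen need among survivors is identical.

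| q | Apparent excess on higher dose | Chance of a significant result in that direction, 71 per arm |
|---|---|---|
| 10% | 1.7 points | 6% |
| 30% | 5.2 points | 11% |
| 60% | 10.4 points | 24% |
| 80% | 13.9 points | 43% |

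If half of the deaths occur before discharge, and all discharged patients have rate q, each excess is halved.

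**4. Survivors only.** With equal q the difference is zero. Suppose instead that everyone who would survive on 6 mg also survives on the higher dose with unchanged oxygen need, and that the extra 17.4% saved leave on oxygen at rate r. The apparent excess is then 0.174(r − q)/0.941. For q from 20% to 50% and r from 60% to 100% this is 1.8 points (q = 50%, r = 60%) to 14.8 points (q = 20%, r = 100%).

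**5. Death or discharge on oxygen.** Every patient who dies or is discharged has a value. Under the assumptions of step 4 the difference is 0.174(1 − r) in favour of the higher dose, so the composite is never worse on that arm and is equal when r = 100%.

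**6. Worked counts.** These use 17 v 4 deaths, hence 54 v 67 survivors. Case A has 30% of survivors on oxygen in each arm (16 and 20). Case B has 16 on oxygen in the 6 mg arm and, with 60% of the 13 extra survivors on oxygen, 16 + 8 = 24 in the higher-dose arm. P-values are uncorrected chi-squared.

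| Handling of deaths | Case A: 6 mg v higher dose | Case B: 6 mg v higher dose |
|---|---|---|
| Coded no oxygen | 16/71 (22.5%) v 20/71 (28.2%), p = 0.44 | 16/71 (22.5%) v 24/71 (33.8%), p = 0.14 |
| Survivors only | 16/54 (29.6%) v 20/67 (29.9%), p = 0.98 | 16/54 (29.6%) v 24/67 (35.8%), p = 0.47 |
| Death or on oxygen | 33/71 (46.5%) v 24/71 (33.8%), p = 0.12 | 33/71 (46.5%) v 28/71 (39.4%), p = 0.40 |

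The direction of the result changes with the handling of deaths alone.

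**The case against.** The strongest reply is that the missing-data rule already reaches this case. If deaths are treated as missing, 21/142 (14.8%) exceeds 5%, and the plan would run both extreme imputations. One of them, all deaths set to oxygen, reproduces the death-or-on-oxygen row above, so the conflict would be visible. That is fair, and it means the plan is not wholly without a safeguard. But the rule does not name death, and death is a known outcome rather than a missing one. The survivors-only result would stay as the reference, with two opposite imputations around it and neither named as the answer.

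A reader might also infer more than the documents support:

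- *The plan scores deaths as successes.* It does not say so; it leaves the coding open.
- *The better the higher dose works, the worse it will score.* This is not general. Survivors-only with equal oxygen rates shows nothing (p = 0.98 in Case A), and coding deaths as oxygen favours the higher dose.
- *The endpoint will contradict the primary result.* None of the worked differences is significant, and all rest on assumed oxygen rates.
- *All 17 v 4 deaths lack a value.* The planned rates are 28-day mortality. Section 20 describes follow-up of patients discharged before day 28 to determine the primary endpoint, so some deaths may come after discharge, and those patients have a valid oxygen status.

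**Conclusion.** The point holds as a gap in the definition of one secondary endpoint. The tested population includes patients for whom the endpoint does not exist, and nothing says how they count. Up to about 17 v 4 of 71 per arm are affected if the planned mortality holds and all deaths precede discharge; fewer if some do not.

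Coding deaths as no oxygen biases the comparison against the higher dose by 0.174 × q, about 2 to 14 points over the assumed range, when all deaths precede discharge. Survivors-only is free of this distortion if oxygen rates are equal, but can look worse for the higher dose if those saved are sicker. The claim is that the endpoint can mislead, not that it will.

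The primary mortality comparison and its sample size are unaffected. This is a cheap improvement rather than a flaw that threatens the trial.

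**What to change.** In Sections 4, 10 and 12, define the tested endpoint in all randomized patients as death before discharge or discharge on supplemental oxygen; equivalently, test its complement, discharge alive without oxygen. State how patients still in hospital at day 28 count. The plan has no rule for them either, and the figures above do not cover them. Report the proportion on oxygen among survivors descriptively. Say that the missing-data rule applies to unknown status and not to deaths.

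The cost is a change of wording. Oxygen at discharge, disposition including death, and length of stay are already collected under Section 11. The downside is that the composite partly overlaps with mortality, so its components should be shown separately. The wording should be settled before outcomes by arm are seen, because choosing the coding afterwards can choose the direction.
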